Our primary aim is to evaluate the impact of the mobility program on mobility in the year after hospital discharge using the UAB Life-Space Assessment (LSA). In our previous small VA-funded study of a mobility intervention, patients in the MP group had a mean LSA score that was approximately 10 points higher than in the UC group at four weeks' post-discharge. It is our expectation that the current study will replicate these results; specifically, that the 10-point difference will be apparent at 1-month post-discharge and persist thereafter. As described below, the primary statistical technique to address the primary aim will be mixed effects models. Assuming an exchangeable covariance structure across the repeated observations, a sample size of 190 participants provides greater than 90% power to detect a persistent 10-point difference in LSA scores at the $\alpha = .05$ level. We must also consider the reduced effective sample size due to clustering. It is a common practice to calculate the intraclass correlation (ICC) among clusters as a measure of how much more similar members of the same cluster are to each other than to the overall population. In this setting, we recognize that subjects at UAB may differ from subjects at the VA, leading to differences in the ICC. However, we still expect much more variability to come from individual patient factors than from the units. Using the data from our recently completed VA longitudinal study, we calculated an ICC for the LSA that rounded to 0; including data from UAB resulted in an ICC approximately 4 times larger. Assuming an ICC of 0.004 and subjects spread across 9 units, a sample size of 206 yields an effective sample size of 190 observations. In our recently completed VA longitudinal study during which patients were followed for 6 months after hospital discharge, 80% of the veterans completed at least 5 of the 6 monthly post-hospital assessments. We had 23 deaths and 3 withdrawals over the 6 months of follow-up among the 200 veterans in the study. Thus, in order to have an adequate (i.e. 206) sample size at 12-months, 258 patients will be enrolled allowing for patient losses due to

death or drop outs. Thus, while adding units from UAB to the study does increase the required sample size slightly due to the larger ICC, this is offset by the larger number of potential subjects that can be recruited.

Analytic Approach (for each specific aim)

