Informed by the modeling of secular trends, the final models will add in indicator terms for whether the observation occurred before or after the intervention, in addition to the appropriate modeling of secular trends. Additional more sophisticated modeling will evaluate the trends in the outcomes over time in the post-intervention periods to see whether temporal trends differ pre-and post- intervention. All statistical tests will be two-sided and will be considered to be significant if the associated p-value is <0.05. All analyses will be intention-to-treat based on the unit’s assignment at the time of a patient’s admission, and missing data will be imputed using a multiple imputation strategy, based on the characteristics of the data.

AIM 1: To test the effectiveness of a mobility program on recovery to pre-hospital mobility status or better and reduction of adverse outcomes in the year after hospitalization.

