Data Safety and Monitoring Board (DSMB) The Data Safety and Monitoring Board will be charged with recommending changes in the study protocol or closure of the study if the incidence of falls or another adverse event in the intervention group at BVAMC is significantly greater than that observed in the control group at BVAMC. The board's membership will include a physician, a physical therapist and a nurse. The DSMB will meet quarterly either in-person or by conference call to discuss the study and any issues or concerns. Incidents will be reported to the DSMB by email.

The following incidents which occur at BVAMC will be reported to the DSMB and IRB immediately:

1. Falls by participants that occur during the inpatient portion of the study
2. Open wounds (Stage II or greater pressure ulcers indicating a breach of the skin's integrity) under the area of the StepWatch

The following incidents which occur at BVAMC will be reported to the DSMB quarterly:

1. Falls by participants that occur after the inpatient portion of the study, but while enrolled, together with statistics on the current fall rate at BVAMC
2. Participants' deaths that occur after the inpatient portion of the study, but while enrolled
3. Emergency department visits that occur after the inpatient portion of the study, but while enrolled
4. Rehospitalizations that occur after the inpatient portion of the study, but while enrolled
5. Participant transferred to ICU/CCU or Safe Harbor during the inpatient portion of the study
6. Participant dies during the inpatient portion of the study
7. Skin irritation in the immediate vicinity of the StepWatch

AEs, SAEs, and other incidents which involve UAB participants will be reported to the UAB IRB.

K. POTENTIAL BENEFITS: Assess the potential benefits to be gained by the individual subject, as well as benefits which may accrue to society in general as a result of the planned work.

For the group of patients who receive the hospital mobility intervention, it is expected they will maintain or improve their mobility to a greater degree than those in the usual care group. As ability to walk is a key component of all basic activities of daily living, the MP group may also experience an improvement in their ADL ability to a greater degree after hospital discharge. As mobility disability is associated with a reduction in quality of life, the MP group may experience an improvement in quality of life.

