Impact of a Hospital Mobility Program on Function after Discharge

Statistical Analysis Plan

Sample Size Calculations: Our primary aim is to evaluate the impact of the mobility program on mobility in the year after hospital discharge. In our previous small VA-funded study of a mobility intervention, patients in the MP group had a mean LSA score that was approximately 10 points higher than in the UC group at four weeks post-discharge. It is our expectation that the current study will replicate these results; specifically that the 10 point difference will be apparent at 1-month post-discharge and persist thereafter. As described below, the primary statistical technique to address the primary aim will be mixed effects models. Assuming an exchangeable covariance structure across the repeated observations, a sample size of 190 participants provides greater than 90% power to detect a persistent 10-point difference in LSA scores at the $\alpha = .05$ level. We must also consider the reduced effective sample size due to clustering. It is a common practice to calculate the intraclass correlation (ICC) among clusters as a measure of how much more similar members of the same cluster are to each other than to the overall population. In this setting, we expect much more variability to come from individual patient factors than from the units. Using the data from our recently completed VA longitudinal study, we calculated an ICC for the LSA that rounded to 0. Assuming a larger ICC of 0.001 and subjects spread across 5 units, a sample size of 198 yields an effective sample size of 190 observations. In our recently completed VA longitudinal study during which patients were followed for 6 months after hospital discharge, 80% of the veterans completed at least 5 of the 6 monthly post-hospital assessments. We had 23 deaths and 3 withdrawals over the 6 months of follow-up among the 200 veterans in the study. Thus, in order to have an adequate (i.e. 198) sample size at 12-months, 226 patients will be enrolled allowing for patient losses due to death or drop outs.

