regularly meet by phone (e.g., Nurse Executives). Finally, we will seek out opportunities to present our findings to frontline staff (e.g., through quality collaboratives or other activities coordinated through the National Center for Patient Safety).

Limitations of the Study: Maintenance of blinding is a potential limitation. It is possible the Assessor will observe the veteran walking, or will be told information about the group assignment by the patient or healthcare provider. We will address this concern in three ways. First, we will regularly encourage the participant not to share their group assignment with the Assessor. In addition, we will provide **all** patients with identical StepWatches®. Lastly, after the patient completes the study, we will ask the Assessor to identify which group they believe the patient was assigned. There is a risk that the walking intervention will lead to adverse outcomes, such as an increase in falls. Our previous pilot study of a mobility intervention demonstrated the intervention group experienced no falls while three falls occurred among patients in the control group. However, despite these positive results, we will make every effort to provide a safe environment for the increased mobility we are proposing by encouraging patients to both recognize and not exceed their mobility capabilities, and by emphasizing that help is readily available and should be requested if needed. We will also provide ambulatory devices to persons who request them and demonstrate safe use. The selection of a Data Safety and Monitoring Board will be critical to help us achieve this objective of the study, i.e. being falls and injury free. (See Human Studies Section for details).

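### The safety board's only stated between-group trigger is an undefined significance criterion, which at a 1–5% inpatient fall risk would probably miss a doubling of inpatient falls at BVAMC

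*Protocol*

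**What the plan says.** **Protocol section J, Data Safety and Monitoring Board.** The board's charge is "recommending changes in the study protocol or closure of the study if the incidence of falls or another adverse event in the intervention group". The condition attached, applied to patients at the VA site only, is that MP incidence "is significantly greater than that observed in the control group at BVAMC". It meets quarterly. Each BVAMC inpatient fall goes to the board and the IRB immediately. Post-discharge falls, deaths, ED visits, rehospitalizations, ICU/CCU or Safe Harbor transfers and skin irritation are reported quarterly. UAB events go to the UAB IRB.

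**Protocol section E, Analytic Approach (same text in the SAP).** The only significance level in either document is the general one: "All statistical tests will be two-sided and will be considered to be significant if the associated p-value is <0.05". It is not stated to govern the board.

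**SAP, Limitations of the Study.** More falls is the example given of harm from walking. The text continues: "The selection of a Data Safety and Monitoring Board will be critical to help us achieve this objective of the study, i.e. being falls and" (the sentence closes by adding freedom from injury).

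**Aim 1, both documents.** The adverse-outcome analyses cover ADLs and IADLs, ED visits, hospitalizations, nursing home admission and death. Falls are collected at every follow-up (Protocol Tables 7–9), but neither aim analyses them.

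**The concern.** The trigger is the only comparison of falls between arms anywhere in the plan, and it is tied to statistical significance. Inpatient falls are the falls most directly exposed to the walking sessions. In a trial of this size there may be only a handful. A significance criterion on a handful of events will usually be silent even when the true rate has doubled.

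The stake is mainly how that silence is read. The SAP already describes a pilot count of no falls against three as a positive result. Its dissemination section intends the trial to inform a standard of care for safe mobility. A non-significant falls comparison could be carried into that claim without an interval showing how much harm remains compatible with the data.

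**Working it through.** **1. The plan's own figures.** The plan states no power for the board's trigger, so only the enrolment figures can be reproduced. "Assuming an ICC of 0.004 and subjects spread across 9 units, a sample size of 206 yields an effective sample size of 190 observations": 206 / [1 + (206/9 − 1) × 0.004] = 189.4, which agrees with 190. Allowing 20% loss, 206 / 0.80 = 257.5, which gives 258. These figures reproduce.

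**2. BVAMC sample size (not stated; assumed range).**
- Lower end: half of 258 = 129.
- Middle: share of ward-months. BVAMC has 5 wards × 35.4 months = 177. UAB has 4 wards × 20 months = 80. 177/257 = 69%, and 69% of 258 is about 178.
- Upper end: the SAP's VA-only plan, in which "226 patients will be enrolled allowing for patient losses due to death or drop outs".

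**3. Allocation.** Figure 4 has 5 wards × 7 periods, of which 20/35 = 57% are on MP. With even accrual, 178 patients split about 76 UC and 102 MP.

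**4. Inpatient fall risk (not stated; assumed).** 1%, 3% and 5% on usual care, with 10% as a sensitivity value. MP risk is set to twice that.

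**5. Expected counts at 178 patients and 3%.** UC: 76 × 0.03 = 2.3 falls. MP with no harm: 102 × 0.03 = 3.1. MP with risk doubled: 102 × 0.06 = 6.1.

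**6. One final Fisher test, two-sided 0.05.** Chance of missing a doubling (1 − power, by exact enumeration):

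| BVAMC patients (UC:MP) | 1% | 3% | 5% | 10% |
|---|---|---|---|---|
| 129 (55:74) | 99.8% | 93.5% | 86.6% | 70.9% |
| 178 (76:102) | 99.2% | 89.4% | 81.3% | 60.8% |
| 226 (97:129) | 98.2% | 85.9% | 76.9% | 49.1% |

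**7. Twelve unadjusted quarterly looks (36 months of recruitment), simulated on the Figure 4 calendar, 130–226 patients, 1–5% risk.**
- Exact conditional comparison (MP falls given total falls, upper tail at most 0.025): misses about 71–99%.
- Fisher test: misses up to about 97%. The lower end is 61–66%, depending on simulation details.
- Uncorrected z-test, 178–226 patients: misses 77–81% at 1% and 51–55% at 5%. It also crosses in 8–16% of trials with no true difference.

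Clustering and adjustment for calendar time are ignored; both would lower power further.

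**8. What a null result would leave open.** At 178 patients with 3% in both arms, the 95% half-width for the risk difference is 1.96 × √[0.03 × 0.97 × (1/76 + 1/102)] = 0.051, about ±5 percentage points. If the observed rate ratio were exactly 1, its upper limit would be exp[1.96 × √(1/3.06 + 1/2.28)] = 5.6.

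**9. All falls over one year.** Assuming a 30% usual-care risk, a doubling to 60% would be found by one Fisher test with power 92% at 130 patients, 98% at 178 and 99% at 226.

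**The case against.** The strongest reply is that the board is not confined to a test. It hears of every BVAMC inpatient fall at once, sees other events quarterly, and has a general remit to discuss problems. The protocol also sets out gait belts, therapist-trained staff and two-person walking. All of this stands. A reader might infer that anything short of p<0.05 obliges the board to continue, or that the plan treats a quiet board as proof of safety. The documents say neither. What remains is that individual reports do not show an excess between arms, and the only stated comparative criterion is the significance one.

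Second, the percentages are not properties of the plan. They depend on a fall risk, a BVAMC sample size and a test that the documents do not give. At a 10% risk the uncorrected z-test over repeated looks, with 178–226 patients, misses only about 29–37%. This stands, so no single figure should be quoted without its conditions.

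Third, the trigger refers to falls generally and to other adverse events. It would usually detect a doubling of all falls (step 9). With 23/200 deaths at six months as the base, it would detect doubled deaths over repeated looks in about 56–78% of trials. The claim that the trigger says little about harm in general is therefore unsupported. So is a claim that it often fires by chance on common events: that depends on event rates not in the documents.

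Fourth, the protocol is dated February 2021 and Figures 4 and 4A end on 12/31/19, so in-trial monitoring may be largely over. The reporting part of the point still applies.

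**Conclusion.** The point holds in limited form. The board's only stated between-group criterion for recommending change or closure is an undefined significance comparison at BVAMC, and no aim analyses falls. With an assumed 1–5% inpatient fall risk, 130–226 BVAMC patients and an exact or Fisher test at two-sided 0.05, a true doubling of inpatient falls would be missed in roughly 65–99% of trials. At a 10% risk a single Fisher test would miss about 50–70%. A non-significant comparison of inpatient falls is therefore weak evidence of safety. The conclusion is confined to inpatient falls. It does not show that the board is blind to harm, or that the plan claims safety from a lack of significance.

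**What to change.** In Protocol section J, remove statistical significance as the precondition for a board recommendation. At each quarterly meeting give the board, by arm, event counts, person-time, and the MP–UC rate difference and rate ratio with 95% confidence intervals. Show inpatient falls and deaths first. Let the board act on these estimates together with its review of individual events, and leave any threshold to the board. A rule that compares the upper confidence limit with a fixed margin at every meeting would not help: with an interval of about ±5 points even at full BVAMC accrual, the limit would exceed any modest margin without true harm.

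In the SAP, add a between-arm falls estimate with its confidence interval to the final analysis. State that a non-significant difference will not be reported as showing no increase in falls.

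The cost is one more table per quarter and a few lines of text, using data already collected. The evidence on inpatient falls will probably have to be reported as inconclusive.

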Impact of a Hospital Mobility Program on Function after Discharge

Statistical Analysis Plan

Sample Size Calculations: Our primary aim is to evaluate the impact of the mobility program on mobility in the year after hospital discharge. In our previous small VA-funded study of a mobility intervention, patients in the MP group had a mean LSA score that was approximately 10 points higher than in the UC group at four weeks post-discharge. It is our expectation that the current study will replicate these results; specifically that the 10 point difference will be apparent at 1-month post-discharge and persist thereafter. As described below, the primary statistical technique to address the primary aim will be mixed effects models. Assuming an exchangeable covariance structure across the repeated observations, a sample size of 190 participants provides greater than 90% power to detect a persistent 10-point difference in LSA scores at the $\alpha = .05$ level. We must also consider the reduced effective sample size due to clustering. It is a common practice to calculate the intraclass correlation (ICC) among clusters as a measure of how much more similar members of the same cluster are to each other than to the overall population. In this setting, we expect much more variability to come from individual patient factors than from the units. Using the data from our recently completed VA longitudinal study, we calculated an ICC for the LSA that rounded to 0. Assuming a larger ICC of 0.001 and subjects spread across 5 units, a sample size of 198 yields an effective sample size of 190 observations. In our recently completed VA longitudinal study during which patients were followed for 6 months after hospital discharge, 80% of the veterans completed at least 5 of the 6 monthly post-hospital assessments. We had 23 deaths and 3 withdrawals over the 6 months of follow-up among the 200 veterans in the study. Thus, in order to have an adequate (i.e. 198) sample size at 12-months, 226 patients will be enrolled allowing for patient losses due to death or drop outs.

Data Management: Data collected from in-hospital assessments will be recorded by the research assistant on paper forms. Forms will be reviewed daily by the project coordinator for errors and completeness relating to the patient identification number and name, legibility of handwriting, appropriate form used, and missing data. The forms will then be entered into an Access database which will be programmed to include multiple error checking techniques for inconsistent data and out of range coding to ensure accuracy of the data entry.

Analytic Approach (for each specific aim):

General: Descriptive statistics including mean, standard deviations, distribution, maximum and minimum values for the study variables will be calculated. Data will be examined graphically and by summary statistics for outliers and distributional properties (e.g., normality, skewness) that may lead to transformations or nonparametric analyses where indicated.

To analyze differences in LSA while accounting for changes in units over time, we will use a stepped-wedge design (Figure 3, above), a variation of cluster randomization in which each cluster is eventually assigned to intervention.⁵⁸ By beginning with a pre-intervention period and implementing the interventions in 'steps' at set times, each unit serves as its own control, with pre-intervention observations used to estimate any underlying long-term or seasonal trends with precision so that effects from the intervention can be distinguished from these 'secular' trends. While the standard stepped-wedge design treats time in discrete blocks (the 'steps'), this trial will

be able to provide more robust estimates of secular trends because observations are linked to the date of each patient's admission, providing a much finer temporal resolution. To understand the secular trends, we will start by examining smoothed plots of LSA over time overall and stratified by unit to identify especially large temporal fluctuations that may indicate unanticipated changes in processes or personnel. We will then model LSA during the time prior to the initiation of the intervention using mixed models,⁵⁹ to account and test for heterogeneity among hospital units (in both means and trends) and possible nonlinearities. While secular trends must be accounted for in the final models, results from this preliminary analysis will inform whether potential trends can be considered to be linear, and whether all units can be considered to have the same trends over time.

Informed by the modeling of secular trends, the final models will add in indicator terms for whether the observation occurred before or after the intervention, in addition to the appropriate modeling of secular trends. Additional more sophisticated modeling will evaluate the trends in the outcomes over time in the post-intervention periods to see whether temporal trends differ pre-and post- intervention. All statistical tests will be two-sided and will be considered to be significant if the associated p-value is <0.05. All analyses will be intention-to-treat based on the unit's assignment at the time of a patient's admission, and missing data will be imputed using a multiple imputation strategy, based on the characteristics of the data.

AIM 1: To test the effectiveness of a mobility program on recovery to pre-hospital mobility status or better and reduction of adverse outcomes in the year after hospitalization.

To test the effectiveness of the intervention on mobility, LSA scores and changes in LSA scores for patients in the control condition will be compared to LSA scores from patients in the intervention condition. Mixed models will be used to examine and compare mean LSA over time with time considered a random effect. An indicator term will be included to denote whether the observation was from the period prior to or after implementation of the intervention. The indicator term will represent whether there was an overall difference in the LSA during the intervention period versus the pre-intervention period, and its statistical significance in the model for each outcome will be the primary test of whether the intervention had a significant effect on LSA. *A priori* we believe that an exchangeable covariance structure will be most suitable for the data. For the secondary hypotheses, i.e., self-reported outcomes for driving (yes/no) and ability to walk ¼ of a mile (yes/no), generalized linear mixed models (GLMMs) that account for repeated measures will be used to compare pre- and post-intervention periods. Given the randomized nature of the study design, adjustment for potential confounders will likely be unnecessary as they are expected to be equally distributed between the groups. However, as noted above, we will confirm that any potential confounders, e.g., age, length of hospitalization, and disease burden score (Cumulative Illness Rating Scale-Geriatrics⁵⁷) are indeed similar between the pre- and post-intervention periods and, should any not be, we will adjust for them in the statistical models provided they are not deemed to be consequences of the intervention.

To test the effectiveness of the intervention on adverse outcomes, we will use mixed models and GLMMs to model changes in functional decline (ADLs and IADLs), number of ED visits, and number of hospitalizations with an approach similar to the above. To test the effectiveness of the intervention on nursing home admission and death, we will use Cox proportional hazards models

to compare the time from hospital discharge to the time to event between the MP and UC groups, adjusting for potential covariates. Due to the potential interrelationship between risk of nursing home admission and risk of death, competing hazards will be used to model the time to occurrence of the first event. Right censoring of participants will occur with dropout due to any reason (death, loss to follow-up, conclusion of the study period, etc.). Multiple imputation techniques will be used to offset potential bias due to missing predictors in the models.

AIM 2: To identify characteristics which modify the effect of the mobility intervention on recovery to pre-hospital mobility status or better and reduction of adverse outcomes in the year after hospitalization. Potential effect modifiers include pre-admission ADL and LSA, cognitive function, level of in-hospital mobility, depressive symptoms, and social support. For continuous variables, e.g., activities of daily living score, overall distributions will be reviewed and categorized as low, medium and high based on tertile cut-points. To test for significant effect modification, single second level interaction terms, combining pre-/post-intervention indicators with potential effect modifiers, will be added to mixed models. Resulting F-tests for the interaction terms will be reviewed and p-values <0.05 identified as significant. Examination of potential effect modifiers based upon their tertile groupings not only allows for the identification of significant factors but also has the added benefit of examining factor's dose effect, providing additional internal validity to the analysis.

Implementation/Dissemination: This research holds great promise as we begin to define a standard of care for hospital mobility, which is currently lacking. With the success of this proposal we will have demonstrated the effectiveness of this program on mobility and adverse outcomes after hospitalization as well as identified patient characteristics that modify the intervention effects. It is critical to develop a robust evidence base for mobility during hospitalization as hospitals all across the country and the world are currently grappling with the issue of low mobility and its consequences. As noted by a recent review by Kalisch, "Interventions and policies that increase inpatient mobilization need to be developed, tested and put into practice."⁶ This study would provide the type of data needed to develop VA policies and a standard of care for safe mobility for all hospitalized veterans. Future steps would include a multicenter trial to assess the generalizability of the program followed by dissemination of the mobility program to VA hospitals across the nation.

We propose a multi-level dissemination plan designed to target research findings to several different audiences. First, we will use traditional dissemination through the publication of high-quality peer-reviewed articles throughout the study's conduct, including empirical, methodological, and theoretical manuscripts. Manuscripts summarizing results will be targeted to (1) management-oriented journals (e.g., Journal of Nursing Management); (2) clinical nursing, physician and physical therapy journals (e.g., Journal of Hospital Medicine); and quality improvement and implementation oriented journals (e.g., Journal of Nursing Care Quality, Implementation Science). We will deliver presentations to research and policy-oriented audiences. It is imperative also that we bring early results to VA-specific audiences including VISN, facility, and nursing leadership; nurse managers, rehabilitation managers and frontline staff. We will use written, oral and web-based dissemination strategies to bring early results to these stakeholders. Examples include reporting through relevant approved Central Office publications (e.g., newsletters, web-based material), as well as reporting to groups of stakeholders who

regularly meet by phone (e.g., Nurse Executives). Finally, we will seek out opportunities to present our findings to frontline staff (e.g., through quality collaboratives or other activities coordinated through the National Center for Patient Safety).

Limitations of the Study: Maintenance of blinding is a potential limitation. It is possible the Assessor will observe the veteran walking, or will be told information about the group assignment by the patient or healthcare provider. We will address this concern in three ways. First, we will regularly encourage the participant not to share their group assignment with the Assessor. In addition, we will provide **all** patients with identical StepWatches®. Lastly, after the patient completes the study, we will ask the Assessor to identify which group they believe the patient was assigned. There is a risk that the walking intervention will lead to adverse outcomes, such as an increase in falls. Our previous pilot study of a mobility intervention demonstrated the intervention group experienced no falls while three falls occurred among patients in the control group. However, despite these positive results, we will make every effort to provide a safe environment for the increased mobility we are proposing by encouraging patients to both recognize and not exceed their mobility capabilities, and by emphasizing that help is readily available and should be requested if needed. We will also provide ambulatory devices to persons who request them and demonstrate safe use. The selection of a Data Safety and Monitoring Board will be critical to help us achieve this objective of the study, i.e. being falls and injury free. (See Human Studies Section for details).
